#### **4.2 Exclusion Criteria**

1. Patient has received prior salvage therapy, including salvage radiotherapy, for relapsed or refractory classical HL
2. Chemotherapy or biologics therapy that is not completed 4 weeks prior to the first dose of study drug(s), unless documented progression of underlying disease on treatment
3. Prior radiation therapy within 3 weeks, or chest radiation  $\leq 12$  weeks prior to first dose of the study drug(s)
4. For patients in Parts 1 and 2, previous treatment with brentuximab vedotin; for Part 3, patients with HL that is refractory to a brentuximab vedotin-containing regimen in first line, or patients who discontinue brentuximab vedotin due to unacceptable toxicity are ineligible. Refractory disease is defined as never achieving a CR to frontline therapy or having a CR but then progressing within 3 months of completing frontline therapy
5. Has received any prior immuno-oncology therapy (e.g., therapies affecting the PD-1, CTLA4, or CD137 pathways)
6. Previously received an allogeneic and/or autologous stem cell transplant for HL
7. Current therapy with other systemic antineoplastic or investigational agents
8. Systemic treatment with either corticosteroids ( $>10$  mg daily prednisone equivalent) or other immunosuppressive medications within 14 days of enrollment
  - Inhaled or topical steroids and adrenal replacement steroid doses  $>10$  mg daily prednisone equivalent, are permitted in the absence of active autoimmune disease
9. History of another primary invasive malignancy that has not been in remission for at least 3 years
10. History of progressive multifocal leukoencephalopathy (PML)

11. Known cerebral/meningeal disease related to the underlying malignancy
12. Pre-existing neuropathy of Grade 2 or greater
13. Any active Grade 3 or higher (per the National Cancer Institute's Common Terminology Criteria for Adverse Events [NCI CTCAE], Version 4.03) viral, bacterial, or fungal infection within 2 weeks prior to the first dose of brentuximab vedotin; routine antimicrobial prophylaxis is permitted
14. Females who are pregnant or breastfeeding
15. Known hypersensitivity to any excipient contained in the drug formulation of brentuximab vedotin or nivolumab
16. Positive for hepatitis B by surface antigen expression, or any other positive test for hepatitis B virus indicating acute or chronic infection
17. Active hepatitis C infection (positive by serology and confirmed by polymerase chain reaction [PCR] or on antiviral therapy for hepatitis C within the last 6 months)
18. Known history of testing positive for human immunodeficiency virus (HIV) or known acquired immunodeficiency syndrome (AIDS)
19. Documented history of a cerebral vascular event (stroke or transient ischemic attack), unstable angina, myocardial infarction, or cardiac symptoms consistent with New York Heart Association Class III-IV ([Appendix C](#)) within 6 months prior to their first dose of study drug(s)
20. Previous history of known or suspected autoimmune disease
  - Patients with type I diabetes mellitus, hypothyroidism only requiring hormone replacement, skin disorders (such as vitiligo, psoriasis, or alopecia) not requiring systemic treatment, or conditions not expected to recur in the absence of an external trigger are permitted
21. Active interstitial lung disease that is symptomatic or may interfere with the detection or management of suspected drug-related pulmonary toxicity
22. Known history of pancreatitis
23. Other serious underlying medical condition that, in the opinion of the investigator, would impair the ability to receive or tolerate the planned treatment and follow-up

#### **4.3 Removal of Patients from Therapy or Assessment**

Seattle Genetics or their designee must be notified if a patient is withdrawn from study treatment or from the study. The reason(s) for withdrawal must be documented in the patient's medical records and case report form (CRF).

#### **4.3.1 Discontinuation of Study Drug**

A patient's treatment with study drug may be discontinued for any of the following reasons:

- Completed treatment
- Progressive disease
- AE
- Investigator decision
- Patient decision, non-AE
- Study termination by sponsor
- Other, Non-AE

Patients who discontinue from study treatment will remain on study for follow-up unless they withdraw consent. Dose delays of both brentuximab vedotin and nivolumab resulting in treatment interruption of all therapy for >6 weeks require patient discontinuation from study treatment.

#### **4.3.2 Patient Withdrawal from Study**

Any patient may be discontinued from the study for any of the following reasons:

- Completed study per protocol
- Patient withdrawal of consent
- Study termination by sponsor
- Lost to follow-up
- Death
- Other

### **5 TREATMENTS**

#### **5.1 Treatments Administered**

There are two investigational agents under study in this protocol. Brentuximab vedotin is an ADC consisting of the antibody cAC10, specific for human CD30; the microtubule-disrupting agent MMAE; and a protease-cleavable linker that covalently attaches MMAE to cAC10. Nivolumab is a fully human IgG4 monoclonal antibody that acts as an immunomodulator by blocking ligand activation of the PD-1 receptor on activated T cells.

#### **5.2 Brentuximab Vedotin**

Detailed information describing the preparation, administration, and storage of brentuximab vedotin is located in the Pharmacy Binder.

##### **5.2.1 Description**

Brentuximab vedotin is a sterile, preservative free, white to off-white lyophilized cake or powder supplied by Seattle Genetics in single-use vials for reconstitution for IV administration. Each vial of the product contains brentuximab vedotin, trehalose, sodium citrate, and polysorbate 80. See the Pharmacy Binder for further information.

### **5.2.2 Dose and Administration**

Brentuximab vedotin 1.8 mg/kg (or 1.2 mg/kg, if recommended by the SMC during Part 1) will be administered every 21 days by IV infusion given over approximately 30 minutes. For patients in Part 3 who were previously treated with brentuximab vedotin and had a dose reduction, dose assignment must be discussed with the medical monitor.

In the absence of infusion-related reactions, the infusion rate for all patients should be calculated in order to achieve a 30-minute infusion period. Brentuximab vedotin must not be administered as an IV push or bolus. Brentuximab vedotin should not be mixed with other medications. When both drugs are administered on Day 1 of the cycle, brentuximab vedotin administration should be completed at least 30 minutes prior to starting administration of nivolumab.

Dosing is based on patient actual body weight. Doses must be adjusted for patients who experience a  $\geq 10\%$  change in weight from baseline. Other dose adjustments for changes in body weight are permitted per institutional standard. An exception to weight-based dosing is made for patients weighing greater than 100 kg; doses will be based on 100 kg for these individuals. Rounding is permissible within 5% of the nominal dose.

### **5.2.3 Dose Modifications**

[Table 1](#) describes the recommended dose modifications for brentuximab vedotin treatment-associated toxicity.

Doses reduced for brentuximab vedotin-related toxicity should not be re-escalated without discussion with the sponsor. Patients who discontinue nivolumab due to an AE may continue treatment with brentuximab vedotin monotherapy to complete the allowable 4 cycles of treatment. If brentuximab vedotin is withheld at the time a cycle of nivolumab is given, once the AE causing the delay of brentuximab vedotin has resolved, administration of brentuximab vedotin should resume on the same schedule with the next cycle of combination therapy. Dose delays of both brentuximab vedotin and nivolumab resulting in treatment interruption of all therapy for  $> 6$  weeks require patient discontinuation from study treatment.

**Table 1: Recommended dose modifications for brentuximab-associated toxicity**

Toxicity	Grade 1	Grade 2	Grade 3	Grade 4
Peripheral neuropathy	Continue at same dose level	Reduce dose to 1.2 mg/kg and resume treatment a	Withhold until toxicity resolves to $\leq$ Grade 2 or baseline, then resume treatment at 1.2 mg/kg a	Discontinue treatment
Non-hematologic (except peripheral neuropathy)	Continue at same dose level	Continue at same dose level	Withhold dose until toxicity is $\leq$ Grade 2 or has returned to baseline, then resume treatment at the same dose level b	Withhold dose until toxicity is $\leq$ Grade 2 or has returned to baseline, then reduce dose to 1.2 mg/kg and resume treatment, or discontinue at the discretion of the investigator a,b,c
Hematologic d	Continue at same dose level	Continue at same dose level	Withhold until toxicity resolves to $\leq$ Grade 2 or baseline, then resume treatment at the same dose level e . Growth factor support (G-CSF or GM-CSF) should be considered for subsequent cycles. If Grade 4 neutropenia recurs despite growth factor support, consider discontinuation or dose reduction to 1.2 mg/kg. a	

G-CSF = granulocyte colony-stimulating factor; GM-CSF = granulocyte macrophage colony-stimulating factor.

a Dose reductions below 1.2 mg/kg are not allowed, and toxicities should be managed with dose delays.

b Patients who develop Grade 3 or 4 electrolyte laboratory abnormalities may continue study treatment without interruption.

c Treatment should be discontinued for patients who experience Grade 4 infusion-related reactions.

d Support with blood product transfusions allowed per institutional standard of care.

e Patients who develop Grade 3 or 4 lymphopenia may continue study treatment without interruption.

### 5.2.4 Storage and Handling

Refrigeration should be set at 2–8°C for storage of vials and solutions containing brentuximab vedotin. The controlled location must be accessible only to the pharmacist, the investigator, or a duly designated person. Brentuximab vedotin does not contain preservatives; therefore, opened and reconstituted vials of brentuximab vedotin should be used as soon as possible. If not used immediately, the in-use storage should not be longer than 24 hours. It is recommended that brentuximab vedotin vials and solutions be protected from direct sunlight until the time of use. Reconstituted vials and solutions must not be shaken.

Drug accountability instructions are provided in the Pharmacy Binder.

### 5.2.5 Packaging and Labeling

Drug product vials may be labeled as brentuximab vedotin, the United States adopted name (USAN) and the International Nonproprietary Name (INN), or as SGN-35, the compound code; the 2 names can be used interchangeably.

### **5.2.6 Preparation**

Brentuximab vedotin vials are provided via single-use containers. Any partially used vials or diluted dosing solutions should be discarded using appropriate institutional drug disposal procedures.

Brentuximab vedotin should be reconstituted with the appropriate amount of Sterile Water for Injection, United States Pharmacopeia (USP) or equivalent (see Pharmacy Binder for details). The vial should be gently swirled until the contents are completely dissolved. The vial must not be shaken. The reconstituted drug product should be inspected visually for any particulate matter and discoloration.

The required volume of reconstituted drug product should be diluted into an infusion bag. The bag should be gently inverted to mix the solution. The bag must not be shaken. Prior to administration, the reconstituted and diluted drug product should be inspected visually for any particulate matter and discoloration.

Detailed drug preparation instructions are provided in the Pharmacy Binder.

## **5.3 Nivolumab**

Detailed information describing the preparation, administration, and storage of nivolumab is located in the Pharmacy Binder.

### **5.3.1 Description**

Nivolumab is a sterile, preservative free, clear to opalescent, colorless to pale-yellow solution supplied by Seattle Genetics in single-use vials for dilution for IV administration. Each single-use vial of the product contains 100 mg/10 mL solution. See the Pharmacy Binder for further information.

### **5.3.2 Method of Procurement**

Nivolumab will be provided by Bristol-Myers Squibb and supplied to the study sites by Seattle Genetics.

### **5.3.3 Dose and Administration**

For patients in Parts 1 and 2, nivolumab will be administered on Day 8 of Cycle 1 and Day 1 of Cycles 2 through 4 of each 21-day treatment cycle. For patients in Part 3, nivolumab will be administered on Day 1 of all 21-day treatment cycles. Patients will receive nivolumab at a dose of 3 mg/kg (or 1 mg/kg, if recommended by the SMC during Part 1) as a 60-minute infusion. When both drugs are administered on Day 1 of the cycle, nivolumab should be administered at least 30 minutes after completing treatment with brentuximab vedotin.

Nivolumab infusions should be administered through an IV line containing a sterile, non-pyrogenic, low protein binding in-line filter (pore size of 0.2 micrometer to 1.2 micrometer). Other drugs should not be co-administered through the same IV line (e.g., brentuximab vedotin).

Dosing calculations should be based on the body weight assessed at baseline. It is not necessary to recalculate subsequent doses if the patient weight is within 10% of the weight used to calculate the previous dose. All doses should be rounded to the nearest milligram.

The Pharmacy Binder contains specific instructions for nivolumab dose calculation, dilution, preparation of the infusion fluid, and administration.

#### **5.3.4 Dose Modifications**

Based on available information, autoimmune complications are the most likely AEs attributable to nivolumab. Dose modifications for AEs are described in this section as well as in Appendix 2 of the nivolumab Investigator's Brochure.

There will be no dose escalations or reductions of nivolumab allowed, unless determined by the SMC to enroll patients to be treated at 1 mg/kg throughout the trial (see Section 3.1.3). Patients who discontinue brentuximab vedotin due to an AE may continue treatment with nivolumab monotherapy to complete the allowable 4 cycles of treatment. If nivolumab is held at the time a cycle of brentuximab vedotin is given, once the AE causing the delay of nivolumab has resolved, administration of nivolumab should resume on the same schedule with the next cycle of combination therapy. Dose delays of both brentuximab vedotin and nivolumab resulting in treatment interruption of all therapy for >6 weeks require patient discontinuation from study treatment. See Section 7.6.1.1 for determining causality.

##### **5.3.4.1 Dose Delays**

Dose delays for nivolumab-related liver function test (LFT) abnormalities are described in Section 5.3.4.3. Otherwise, nivolumab administration should be delayed for the following:

- Any  $\geq$  Grade 2 non-skin, nivolumab-related AE, with the following exception:
  - Grade 2 nivolumab-related fatigue or laboratory abnormalities, other than LFT abnormalities (see Section 5.3.4.3), do not require a treatment delay
- Any Grade 3 skin, nivolumab-related AE
- Any Grade 3 nivolumab-related laboratory abnormality, other than LFT abnormalities (see Section 5.3.4.3), with the following exceptions for lymphopenia or asymptomatic amylase or lipase:
  - Grade 3 lymphopenia does not require dose delay
  - Any  $\geq$  Grade 3 nivolumab-related amylase or lipase abnormality that has been evaluated clinically and radiographically and is without evidence of pancreatitis does not require dose delay. The medical monitor should be consulted for such  $\geq$  Grade 3 amylase or lipase abnormalities
- Any AE, laboratory abnormality, or intercurrent illness which, in the judgment of the investigator, warrants delaying the dose of nivolumab

Patients who require delay of nivolumab should be re-evaluated weekly or more frequently if clinically indicated. Nivolumab may be resumed at the next scheduled treatment cycle if the AE recovers to  $\leq$  Grade 1 or baseline, with the following exceptions:

- Patients may resume nivolumab treatment in the presence of Grade 2 fatigue
- Patients who have not experienced a Grade 3 nivolumab-related skin AE may resume nivolumab treatment in the presence of Grade 2 skin toxicity
- Nivolumab-related pulmonary toxicity, diarrhea, or colitis must have resolved to baseline before nivolumab treatment is resumed. Patients with persistent Grade 1 pneumonitis after completion of a steroid taper over at least 1 month may be eligible for continued nivolumab treatment if discussed with and approved by the medical monitor
- Nivolumab-related endocrinopathies adequately controlled with only physiologic hormone replacement may resume nivolumab treatment after consultation with the medical monitor

#### **5.3.4.2 Dose Discontinuation**

Dose discontinuations for LFT abnormalities are described in Section 5.3.4.3. Otherwise, nivolumab treatment should be permanently discontinued for the following:

- Any Grade 2 nivolumab-related uveitis, eye pain, or blurred vision that does not respond to topical therapy and does not improve to Grade 1 severity within 6 weeks or requires systemic treatment
- Any Grade 3 non-skin, nivolumab-related AE lasting more than 7 days, with the following exceptions for laboratory abnormalities other than LFT abnormalities (see Section 5.3.4.3), nivolumab-related uveitis, pneumonitis, bronchospasm, hypersensitivity reactions, infusion reactions, and endocrinopathies:
  - Grade 3 nivolumab-related uveitis, pneumonitis, bronchospasm, hypersensitivity reaction, or infusion reaction of any duration requires discontinuation
  - Grade 3 nivolumab-related endocrinopathies adequately controlled with only physiologic hormone replacement do not require discontinuation
  - Grade 3 nivolumab-related thrombocytopenia lasting more than 7 days or associated with bleeding; other Grade 3 nivolumab-related laboratory abnormalities other than LFT abnormalities (see Section 5.3.4.3), do not require treatment discontinuation
- Any Grade 4 nivolumab-related AE or laboratory abnormality other than LFT abnormalities (see Section 5.3.4.3), except for the following events:
  - Grade 4 neutropenia  $\leq$  7 days
  - Grade 4 lymphopenia or leukopenia

- Isolated Grade 4 amylase or lipase abnormalities not associated with symptoms or clinical manifestations of pancreatitis; consult the medical monitor for Grade 4 amylase or lipase abnormalities
- Isolated Grade 4 electrolyte imbalances/abnormalities not associated with clinical sequelae and are corrected with supplementation/appropriate management within 72 hours of their onset
- Grade 4 nivolumab-related endocrinopathy AEs, such as adrenal insufficiency, adrenocorticotrophic hormone deficiency, hyper- or hypothyroidism, or glucose intolerance, which resolve or are adequately controlled with physiologic hormone replacement (corticosteroids, thyroid hormones) or glucose-controlling agents, respectively, may not require discontinuation after discussion with the medical monitor
- Any AE, laboratory abnormality, or intercurrent illness which, in the judgment of the Investigator, presents a substantial clinical risk to the patient with continued nivolumab dosing

Any event that leads to delay in nivolumab dosing lasting >6 weeks from the previous nivolumab dose requires discontinuation of nivolumab treatment, with the following exceptions:

- Dosing delays to allow for prolonged steroid tapers to manage nivolumab-related AEs are allowed. Prior to re-initiating nivolumab treatment in a patient with a nivolumab dosing delay lasting >6 weeks from the previous nivolumab dose, the medical monitor must be consulted. Tumor assessments should continue as per protocol even if nivolumab dosing is delayed. Periodic study visits to assess safety and laboratory studies should also continue every 6 weeks or more frequently if clinically indicated during such dosing delays.
- Dosing delays lasting >6 weeks from the previous nivolumab dose that occur for non-nivolumab-related reasons may be allowed if approved by the medical monitor. Prior to re-initiating nivolumab treatment in a patient with a nivolumab dosing delay lasting >6 weeks, the medical monitor must be consulted. Tumor assessments should continue as per protocol even if nivolumab dosing is delayed. Periodic study visits to assess safety and laboratory studies should also continue every 6 weeks or more frequently if clinically indicated during such dosing delays.

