## **5.4 Required Premedication and Postmedication**

Routine premedication should not be administered for the prevention of infusion-related reactions prior to the first dose of study drug(s).

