#### **5.4.2 Patients in Part 3**

Prophylactic premedication with antihistamines for prevention of infusion-related reactions is to be administered prior to combination treatment on Day 1 of each 21-day cycle beginning with Cycle 1. Antihistamines (e.g., diphenhydramine 50 mg IV or equivalent and famotidine 40 mg IV or equivalent) should be given at least 30 minutes prior to infusion of brentuximab vedotin. Patients who experience an infusion-related reaction with this premedication regimen should receive additional premedication with dexamethasone 0.2 mg/kg (maximum 10 mg IV or equivalent) for all subsequent cycles.

Additional premedications for symptom management (e.g., acetaminophen and/or ondansetron) may also be given at the discretion of the investigator.

If treatment with nivolumab or brentuximab vedotin is discontinued, premedications may be reduced or stopped at the discretion of the investigator during single-agent treatment for subsequent cycles.

Patients should be individually evaluated to assess the need for tumor lysis prophylaxis prior to the first dose of brentuximab vedotin. Patients should receive prophylaxis as appropriate per the institutional standards.

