#### **5.6.1.1 Patients in Parts 1 and 2**

Premedication for the prevention of infusion reactions should be administered beginning with Cycle 2, at least 30 minutes prior to dosing study drug(s), and should include an antihistamine and low-dose corticosteroid, as described in Section [5.4.1](#). If the onset of a reaction occurs during an infusion, the infusion may be interrupted for treatment of the infusion-related reaction, including treatment with antihistamines, corticosteroids, bronchodilator therapy, and/or antipyretics, as appropriate. Patients who experience a Grade 3 infusion-related reaction to brentuximab vedotin or nivolumab may potentially receive additional treatment with the study drug(s) at the discretion of the investigator after discussion with the sponsor.

If anaphylaxis or a Grade 4 infusion-related reaction occurs, administration of the implicated agent(s) (brentuximab vedotin and/or nivolumab) should be immediately and permanently discontinued.

In case of late-occurring hypersensitivity symptoms to nivolumab (e.g., appearance of a localized or generalized pruritus within 1 week after nivolumab treatment), symptomatic treatment may be given (e.g., oral antihistamine or corticosteroids).

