Peripheral Neuropathy (PN) is defined by the peripheral neuropathy MedDRA SMQ broad search. The incidence of PN at baseline will be summarized. The incidence of treatment-emergent and treatment-related PN will each be summarized by preferred term and severity. The incidence of PN leading to treatment discontinuation or requiring dose modification will be summarized. Time to onset, resolution, and improvement of PN events will be summarized.

Subjects with any event of treatment-emergent PN will be categorized into groups according to the following criteria:

- Resolution of all events
- At least 1 event resolved, but all other peripheral neuropathy events did not improve
- Improvement of at least one event
 - All events either improved or resolved
 - Some events improved, some events resolved and some events neither improved nor resolved
 - Some events improved but no events resolved
- No improvement or resolution of any events

The number of subjects will be summarized for the categories defined as above. The incidence of treatment-emergent motor neuropathy will be summarized by preferred term and severity. Time to resolution and improvement of motor neuropathy events will be summarized.

Infusion related reactions

Infusion related reactions (IRR) are defined as any event indicated as IRR by the investigator. The incidence of IRR will be summarized by preferred term and severity. The incidence of IRR leading to treatment discontinuation or requiring dose modification will be summarized for each infusional study drug component. The number of cycles of treatment to first onset of IRR will be summarized.

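### Protocol 5.3.4.2 forbids nivolumab after a Grade 3 infusion reaction, 5.6.1.1 and 5.6.1.2 allow it, and nothing says which rule prevails

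*Protocol*

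**What the plan says.** Protocol 5.3.4.2 (Dose Discontinuation) lists the events, other than liver function abnormalities, after which nivolumab is to be stopped for good. One entry reads: "Grade 3 nivolumab-related uveitis, pneumonitis, bronchospasm, hypersensitivity reaction, or infusion reaction of any duration requires discontinuation". It carries no exception, no discretion and no route through the medical monitor.

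Protocol 5.6.1.1, on managing infusion reactions in Parts 1 and 2, says: "Patients who experience a Grade 3 infusion-related reaction to brentuximab vedotin or nivolumab may potentially receive additional treatment with the study drug(s"), at the investigator's discretion and after discussion with the sponsor. The next paragraph sets the mandatory stop: "If anaphylaxis or a Grade 4 infusion-related reaction occurs, administration of the implicated agent(s) (brentuximab vedotin and/or nivolumab) should be immediately and permanently discontinued". Protocol 5.6.1.2 repeats both statements for Part 3.

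For brentuximab vedotin, footnote c of Protocol Table 1 says: "Treatment should be discontinued for patients who experience Grade 4 infusion-related reactions". Protocol 5.2.3 covers the patient who loses nivolumab: "Patients who discontinue nivolumab due to an AE may continue treatment with brentuximab vedotin monotherapy to complete the allowable 4 cycles of treatment".

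SAP 7.6.1.1 relies on the outcome of these decisions: "The incidence of IRR leading to treatment discontinuation or requiring dose modification will be summarized for each infusional study drug component".

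**The concern.** A site treating a severe reaction to nivolumab has to decide whether the drug may be given again. One section says no. The section headed for infusion reactions, which is where the site would naturally look, says possibly yes. A patient could therefore be re-exposed after a severe reaction despite a stopping rule written as mandatory. The required sponsor discussion is a safeguard, but the sponsor has no single written rule to apply in that discussion.

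There is also a reporting consequence. The same rechallenge is compliant under 5.6.1 and a deviation under 5.3.4.2. Later nivolumab exposure, recurrent reactions and reaction-related discontinuations could then differ between sites for reasons unrelated to the drug. Adverse events are a primary endpoint (Protocol 2.4.1), and the SAP tabulates these discontinuations separately for each drug.

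**Working it through.** **Comparing the texts.** All are current Amendment 4 wording.

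| Event | Protocol 5.3.4.2 | Protocol 5.6.1.1 and 5.6.1.2 | Protocol Table 1, footnote c | Agreement |
|---|---|---|---|---|
| Grade 3 reaction to nivolumab | Permanent stop, any duration | More study drug possible after sponsor discussion | Not applicable | **Conflict** |
| Grade 4 reaction to nivolumab | Permanent stop | Permanent stop | Not applicable | Consistent |
| Grade 3 reaction to brentuximab vedotin | Not applicable | More study drug possible after sponsor discussion | No mandatory stop | Consistent |
| Grade 4 reaction to brentuximab vedotin | Not applicable | Permanent stop | Stop | Consistent |

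The conflict is confined to one cell: Grade 3, nivolumab. Stopping nivolumab there satisfies both texts; the clash appears only when rechallenge is considered.

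**Is discretion implied in 5.3.4.2?** No. Where Section 5.3.4 wants discretion it says so: medical monitor involvement is written in for controlled Grade 4 endocrinopathies (5.3.4.2), persistent Grade 1 pneumonitis (5.3.4.1) and nivolumab delays beyond 6 weeks (5.3.4.2). The infusion-reaction entry has nothing of the kind.

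**Is there a tie-breaker?** No. Section 5.3.4.2 cross-refers only to 5.3.4.3, on liver tests. Sections 5.6.1, 5.6.1.1 and 5.6.1.2 do not refer to 5.3.4.2, and the SAP is silent.

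**How many patients.**

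- Patients on whom a correction can still act: n = 30, the planned size of Part 3. SAP Section 4 records that Parts 1 and 2 had finished enrolling when Part 3 was added.
- Probability p of a Grade 3 nivolumab infusion reaction per patient: not in the documents. Assumed range 0.5% to 5%.
- Expected number affected = n × p. Chance of at least one = 1 − (1 − p)^30.

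| Assumed p | Expected affected of 30 | Chance of at least one |
|---|---|---|
| 0.5% | 0.15 | 14.0% |
| 1% | 0.3 | 26.0% |
| 2% | 0.6 | 45.5% |
| 5% | 1.5 | 78.5% |

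The only infusion-reaction figure for the combination in the documents is 1 reaction of unstated grade among 10 patients in an external study (Protocol 3.2.3). Its exact 95% interval is 0.3% to 44.5%, and it does not give a Grade 3 rate.

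**Doses at stake.** Four nivolumab doses are planned. After a reaction at the first, 4 − 1 = 3 remain, so at most 3 per affected patient.

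**The case against.** Four points can be made for the plan.

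1. *The protocol indicates where to look.* The opening of 5.3.4 says nivolumab dose modifications are described there and in Appendix 2 of the nivolumab Investigator's Brochure, and 5.3.4.2 is the drug-specific section. This favours 5.3.4.2, but it only locates the rules and does not say they override 5.6.1. The Brochure is not among the documents, so whether it settles the matter cannot be checked.

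2. *The texts can be reconciled.* The further treatment allowed in 5.6.1 might mean only the drug that did not cause the reaction, since the protocol elsewhere allows single-agent continuation. The text does not say this. Continuing the tolerated drug is already permitted in 3.1.1, 3.1.2, 5.2.3 and 5.3.4 without sponsor discussion, so the Grade 3 sentence would add little. The next paragraph stops the implicated drug at Grade 4 or anaphylaxis, which implies that it need not stop at Grade 3.

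3. *Rechallenge is gated.* It needs investigator judgement and sponsor discussion. Section 5.3.4.1 delays nivolumab until recovery, 5.3.4.2 stops it whenever the investigator sees substantial clinical risk, and 5.4.1 and 5.4.2 step up premedication after a reaction. This stands, and it limits the likely harm. It does not supply the missing rule.

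4. *The size is small and rests on an assumed rate.* This also stands. The 14% to 79% range largely reflects the chosen limits for p.

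**Conclusion.** The inconsistency is real and should be fixed. For a Grade 3 nivolumab infusion reaction the protocol both requires permanent discontinuation and allows further treatment, with no statement of precedence.

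Its reach is narrow: on the assumed rates, between a fraction of one patient and one or two patients in Part 3. The incidence, grade and cycle of the index reaction are unaffected, as are the sample size and the primary test of CR rate. What is affected is the decision to re-expose a patient after a severe reaction, and how the resulting exposure, discontinuations and deviations are classified. Confidence is high on the textual conflict. Its practical frequency is unknown, and the Brochure appendix could not be consulted.

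**What to change.** State one rule in all three sections:

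- In 5.6.1.1 and 5.6.1.2, limit the Grade 3 further-treatment sentence to brentuximab vedotin, in line with Table 1 footnote c, and refer Grade 3 nivolumab reactions to 5.3.4.2.
- Add that 5.3.4.2 governs nivolumab when a reaction is attributed to both drugs. This matters in Part 3, where both are given on the same day from Cycle 1.
- If the clinical team prefers to permit rechallenge, amend 5.3.4.2 instead and state the conditions there.

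The stricter rule costs the few affected patients the option of nivolumab rechallenge; they may still complete four cycles on brentuximab vedotin alone. The change needs one clarification letter or a few sentences in the next amendment. Design, sample size and analysis stay as they are, and no new SAP flag is needed because deviations (SAP 7.3), dose modifications (SAP 7.4) and reaction-related discontinuations (SAP 7.6.1.1) are already summarised.

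As a purely editorial matter, the same letter could limit the opening sentence of Protocol 5.4, on withholding premedication before the first dose, to Parts 1 and 2. Section 5.4.2 already makes the Part 3 intent clear.
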